4.5 Analysis Sets

With regard to analysis of data, the following analysis sets are defined:

- **Safety Analysis Set (SAF):** All subjects who received at least one dose of the study IMP or Placebo. Individual data will be summarized as treated.
- **Full Analysis Set (FAS):** All patients enrolled (randomized) in the study. Patients will be analyzed as randomized.
- **Per-Protocol Set (PPS):** All subjects in the FAS without any major protocol deviations* as described in Section 10.9 of the Clinical Study Protocol (CSP) and who also satisfy both of the following constraints:
 1. Have at least completed one CGI-S A/A assessment at *Weeks 8-12*
 2. Have at least completed one BPDCL assessment at *Weeks 8-12*Individuals in the PPS population will be analyzed as treated.

*Important violations of eligibility criteria and other deviations from the protocol will be assessed in cooperation with the Sponsor. Important deviations from the protocol may lead to exclusion of a subject from the PPS (See Blinded data review below).

Primary efficacy analysis will be performed using the FAS. Patients will be analyzed as per randomized treatment. Sensitivity and supplementary analyses will be performed in the FAS. Efficacy will also be tested in the PPS analysis will be for descriptive purposes only.

The safety summaries and analyses will be based on SAF. The PPS may be used for additional safety analysis.

Before database lock, protocol deviation and analysis set outputs will be produced and will be sent to Oryzon for review. Analysis Set classifications will be discussed during the Blinded Data Review Meeting to decide which subjects and/or subject data will be excluded from certain analyses. Decisions made regarding the exclusion of subjects and/or subject data from analyses will be made prior to unblinding and will be documented and approved by Oryzon.

A summary of patients (counts and frequencies) in each analysis set, including reasons for exclusion, will be produced in addition to a listing of analysis set assignments by patient, including any reasons for exclusion.

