4.6 Estimands

Summary of primary estimand:

1. In study participants with adult BPD, what is the effect of treatment taken for 12 weeks relative to placebo during the double-blind phase, in the protocol-defined FAS study population as measured by the primary endpoints Clinical Global Impression-Severity focused on agitation/aggression (CGI-SS A/A) and Borderline Personality Disorder Checklist (BPDCL).

2. *Objective*

An estimate of effectiveness which would potentially be supportive of registration. Clinically meaningful effects greater than or equal to 0.2 will be supportive of proof of concept.

3. *Estimand*

- A. The population is the FAS as defined by the protocol's inclusion and exclusion criteria.
- B. Effectiveness is measured using an MMRM to estimate change from baseline over 8-12 weeks in the primary endpoints (CGI-SS A/A and BPDCL).
- C. The treatment evaluated is the randomized treatment as it was assigned to study participants. All types of intercurrent events are incorporated using a treatment policy strategy, which evaluates the randomized treatment as taken including missed or modified treatments, treatment discontinuation, and concurrent treatments. Deaths due to treatment are not expected during the treatment period. A hypothetical strategy will be used to account for the intercurrent event of early study termination to estimate the effect anticipated if all patients had completed the study.
- D. The mean change from baseline between treatment and control arms on the primary endpoints will be estimated over visits associated with 8 -12 weeks of treatment. The study is controlled at a 5% level. The Hochberg correction will be applied. If one endpoint is below the 2.5% level or if both endpoints are below the 5% level of significance the study is declared a success. Intercurrent events that are expected to occur include early treatment discontinuation due to patient choice or due to adverse events both unrelated and related to the medication or study indication (e.g., COVID-19).

4. *Primary estimator and missing data.*

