5.1.1 Primary Efficacy Variable – CGI-S A/A

All available data will be included in the analysis.

This section covers the primary analyses of CGI-S A/A and BDPCL as well as the secondary endpoints of change over time for the same assessment.

The primary endpoints for the assessment of efficacy are the change from baseline to *Weeks 8-12* in CGI-S A/A and BDPCL. Results will be summarized by treatment and visit in terms of absolute values and changes from baseline. Besides summarizing the numerical values, the number and frequency of patients at each value on the scale will be displayed (from 1 to 7).

Boxplots of changes in CGI-S A/A will be presented by treatment arm versus each visit. In addition, individual and mean absolute values and changes from baseline will be plotted versus week.

A shift table will be produced for CGI-S A/A displaying the frequencies and proportions for the following

- At *Weeks 8-12* separately as well as an **combining the model estimates** of the endpoint values over 8-12 weeks:
 - Any decrease
 - Any increase
 - A decrease of at least 3 points
 - An increase by at least 3 points
- Any post-baseline value higher than the baseline
- Any post-baseline value lower than the baseline

The effect of treatment in terms of the change from Baseline to *Weeks 8-12* in CGI-S A/A and BDPCL will be analyzed using a likelihood-based mixed effects model for repeated measures (MMRM) with changes from baseline to each post-baseline visit as the dependent variable and the following factors:

Fixed Factors:

- Site (SITEGR1)
- Visit (AVISITN)
- Treatment Arm (TRT01P)
- Interaction between Visit and Treatment Arm
- Baseline value of the response variable*
- Psychotherapy at baseline (yes/no) (PSYBLYN)*
- Psychotherapy by baseline interaction*

*Interactions with time (visit) will be included for all covariates listed above.

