The random effect of subject will be accounted for via the within-subject error correlation structure. The preferred covariance structure for the model will be unstructured (UN in SAS). If this analysis fails to converge, the model will be simplified first to Heterogeneous Toeplitz (TOEPH), then first order autoregressive with heterogeneous variance (ARH1), then compound symmetry with heterogeneous variance (CSH), followed by compound symmetry (CS). The first (co)variance structure yielding convergence will be used as the primary analysis. If a structured covariance matrix is used the sandwich estimator will be implemented to account for potential correlation matrix misspecification. The degrees of freedom will be calculated using the general Kenward-Roger approximation.

The SAS code for the primary analysis is as follows:

```
PROC MIXED data=adqs;
CLASS TRT01P(REF='Placebo') AVISITN(REF='3') SITEGR1(REF='01') PSYBLFL USUBJID;
MODEL CHG= SITEGR1 AVISITN TRT01P AVISITN*TRT01P STDBASE STDBASE*AVISITN PSYBLFL
STDBASE*PSYBLFL /s SOLUTION CL DDFM = KenwardRoger;
REPEATED AVISITN/ SUBJECT= USUBJID TYPE=UN;
LSMEANS TRT01P*AVISITN /at STDBASE=0 PDIFF CL;
ESTIMATE \see below\
Run;
```

Estimates statements averaging visits 6-8 are as follows:

Vafidemstat LSMEANS

```
ESTIMATE 'TRT01P{Vafidemstat} AVISITN{AVG 6-8}'
INTERCEPT 1
AVISITN 0 0 0.33333 0.33333 0.33333 0
TRT01P 1 0
AVISITN*TRT01P 0 0 0.33333 0.33333 0.33333 0 0 0 0 0 / e cl;
```

Placebo LSMEANS

```
ESTIMATE 'TRT01P{Placebo} AVISITN{AVG 6-8}'
INTERCEPT 1
AVISITN 0 0 0.33333 0.33333 0.33333 0
TRT01P 0 1
AVISITN*TRT01P 0 0 0 0 0 0 0 0.33333 0.33333 0.33333 0 / e cl;
```

LSDiff (Vafidemstat – Placebo)

```
ESTIMATE 'TRT01P{Vafidemstat} AVISITN{AVG 6-8} _TRT01P{Placebo} _AVISITN{AVG 6-8}'
TRT01P 1 -1
AVISITN*TRT01P 0 0 0.33333 0.33333 0.33333 0 0 0 -0.33333 -0.33333 -0.33333 0 / e cl;
```

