5.1.1.1 Sensitivity Analysis

Sensitivity analysis for the CGI-S A/A will focus on the following areas:

Estimate over 8-12 week visits

To assess the degree to which estimating across visits represents the overall effect observed, the primary analysis will be repeated for visits 8, 10, and 12 separately. The combined estimate approach will be revisited if the individual visit analyses are not directionally consistent or if this approach is determined to change the direction of the outcome effect, i.e. one visit is driving the overall effect in the primary analysis (ex: one visit significantly favors treatment, while the other two show no effect or favor placebo).

Analysis Population

The primary analysis will be repeated using the PPS for descriptive purposes only.

Missing Values: Multiple Imputation

To conduct further sensitivity analysis intercurrent events like discontinuation of treatment or patient withdrawal, will be imputed. The PROC MI procedure in SAS will be used to do predictive mean matching using linear regression models ([2]). Imputation will be performed after window mapping. The data at each week will be predicted only using data from the previous weeks. The following SAS model will be used:

```
proc mi data=manual nimpute=30 out=MI1 seed= 123456;
  class trt;
  var trt baseline week2 week4 week6 week8 week10 week12;
  fcs regpmm (week2 = baseline trt baseline*trt /details);
  fcs regpmm (week4 = baseline trt baseline*trt week2 week2*trt /details);
  fcs regpmm (week6 = baseline trt baseline*trt week2 week2*trt week4 week4*trt
/details);
  fcs regpmm (week8 = baseline trt baseline*trt week2 week2*trt week4 week4*trt
week6 week6*trt /details);
  fcs regpmm (week10 = baseline trt baseline*trt week2 week2*trt week4 week4*trt
week6 week6*trt week8 week8*trt /details);
  fcs regpmm (week12 = baseline trt baseline*trt week2 week2*trt week4 week4*trt
week6 week6*trt week8 week8*trt week10 week10*trt /details);
run;
```

Here, baseline is the baseline measurement, and week x is the result of the measurement for Week x . Trt is an indicator variable for the received treatment.

Imputed values that fall outside of the possible range of the test variable will be set to the min or max possible score for the test before imputation.

The following simplifications will be attempted if the model fails to converge for any reason:

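### The imputation step of the missing-data sensitivity analysis (SAP 5.1.1.1) uses received treatment and omits baseline psychotherapy, while the analysis it feeds uses randomised arm and includes psychotherapy

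*SAP*

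**What the plan says.** **Imputation step (SAP 5.1.1.1, Multiple Imputation).** Thirty datasets are created by predictive mean matching ("proc mi data=manual nimpute=30 out=MI1 seed= 123456"). The variables are listed as "var trt baseline week2 week4 week6 week8 week10 week12", and the first equation is "fcs regpmm (week2 = baseline trt baseline*trt /details". Later equations add only earlier visit scores and their products with `trt`. The text below the code states "Trt is an indicator variable for the received treatment".

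**Analysis step (SAP 5.1.1, reused in 5.1.1.1).** The mixed model of 5.1.1 is fitted to every imputed dataset and the results are pooled. Its model statement begins "MODEL CHG= SITEGR1 AVISITN TRT01P AVISITN*TRT01P STDBASE STDBASE*AVISITN PSYBLFL" and goes on to a baseline-by-psychotherapy term. The covariate list in the same section includes "Psychotherapy at baseline (yes/no) (PSYBLYN").

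**Estimand and analysis set.** SAP 4.6 states "The treatment evaluated is the randomized treatment as it was assigned to study participants". For the FAS, which is everyone randomised, SAP 4.5 states "Patients will be analyzed as randomized". It also places the sensitivity analyses in the FAS.

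**Two descriptions of the imputation.** SAP 4.6 describes imputation done separately by arm, plus a run relative to the placebo group only. SAP 5.1.1.1 describes a run on all participants across arms, plus a run based on placebo only.

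**The concern.** A missing-data sensitivity analysis is useful when it changes the missing-data assumption and nothing else. Here the values are filled in under one treatment variable and covariate set, then analysed under another. If the pooled result differs from the primary result, three explanations compete: the missing-data assumption, the switch from randomised to received treatment, and the dropped covariate.

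Psychotherapy is not an arbitrary covariate in this trial. Under Protocol 3.1, 4.2 and 6.1.1, starting psychotherapy leads to discontinuation, and stopping it is listed as a possible reason for withdrawal. Baseline psychotherapy status therefore determines which of these exits is open to a participant. The mixed model conditions on that status and the imputation model does not, so the missing-at-random run makes a somewhat different missing-at-random assumption from the primary analysis.

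**Working it through.** **1. The two steps side by side**

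| | Imputation (5.1.1.1) | Analysis of each imputed dataset (5.1.1) |
|---|---|---|
| Treatment | `trt`, received | TRT01P, planned arm |
| Baseline score | yes, and by `trt` | yes, and by visit |
| Earlier visit scores | yes, and by `trt` | through the within-subject covariance |
| Psychotherapy at baseline | no | yes, and by baseline |
| Site | no | yes (pooled) |

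**2. Participants randomised but never dosed.** The FAS holds everyone randomised; the Safety Analysis Set holds only those with at least one dose (SAP 4.5). Someone in the first set but not the second has no received treatment, and the SAP does not say what `trt` is for that person. The SAP does treat the two concepts as distinct: SAP 4.4.1 lists randomised and actual treatment separately.

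**3. Placebo-only run.** SAP 4.6 uses this run as a lower bound on the effect. With `trt` defined as received treatment, its reference group is received placebo, while the contrast compares randomised arms.

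**4. By arm or across arms.** Every predictor in the code is multiplied by `trt`, so the regression coefficients may differ by arm. All participants nevertheless enter one procedure, and nothing in the code restricts matching donors to the same arm. The code therefore sits between the two descriptions in the text.

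**5. Scale, from the plan's own figures (SAP 4.7).** Effect 0.51, two-sided alpha 0.025, power 80%:

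- n per arm = 2 × (2.2414 + 0.8416)² / 0.51² = 2 × 9.505 / 0.2601 = 73.1, so 74. The t-test version gives 74.4, so 75. Power with 75 per arm is 81.1%.
- 75 / 0.8 = 93.75, so 94 per arm and 188 in total.

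The plan's figures reproduce. Planned dropout is 188 − 150 = 38 participants, counted to Visit 9 (Week 14). The share with imputed scores at Weeks 8–12 is not given.

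**6. Illustrative simulation.** These inputs are assumptions, not document figures: ten sites, half the participants in psychotherapy, 18–20% dropout without return, and 10 imputations (the SAP plans 30). There were 188 participants, a true effect of 0.51 and 400 trials per row. The Weeks 8–12 average was analysed by regression on arm, baseline, psychotherapy and site. The comparator imputation used randomised arm, psychotherapy and site, which is a larger change than the one proposed under the fix.

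| Scenario | Full data | As written | Comparator | Difference |
|---|---|---|---|---|
| Dropout on prior scores, psychotherapy effect 0.3 | −0.513 | −0.503 | −0.498 | 0.005 |
| Same, 2 of 188 misdosed | −0.495 | −0.486 | −0.481 | 0.005 |
| Same, 9 of 188 misdosed | −0.460 | −0.454 | −0.450 | 0.004 |
| No psychotherapy effect | −0.504 | −0.491 | −0.486 | 0.005 |
| Dropout on psychotherapy, opposite by arm, effect 0.5 | −0.503 | −0.441 | −0.474 | 0.033 |

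Standard errors were 0.137 to 0.140. In the first four rows the comparator was not closer to the full-data value. In the last row it recovered 0.033 of a shortfall of 0.503 − 0.441 = 0.062, about half, and the shift was 0.033 / 0.14 = 0.24 of a standard error. Changing only received to randomised arm, without covariates, moved the mean by 0.001 or less with 2 or 9 misdosed.

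**The case against.** **The analysis step is sound.** A reader might infer that the whole sensitivity analysis departs from the FAS model, or is analysed as treated. The documents do not support that. SAP 5.1.1.1 fits the 5.1.1 model to each imputed dataset, so the tested contrast remains by randomised arm, adjusted for site and psychotherapy. This objection stands, and the point is confined to the imputation step.

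**Psychotherapy is partly carried already.** A reader might also infer that imputed values contain no psychotherapy effect. That is too strong. Each equation uses baseline and all earlier scores, and participants are required to keep their psychotherapy status (Protocol 6.1.1), so a stable effect is largely in those scores. What is lost is the remainder given the score history. The remainder matters more for participants with few or no post-baseline scores, and under the second convergence fallback, which drops the earlier scores.

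**Received and randomised arm may coincide.** Allocation is by IWRS with numbered kits (Protocol 5.1.5, 5.1.3), and no document forecasts misdosing. The word may simply be loose. This stands as to size, but it leaves the never-dosed unresolved. The Protocol Synopsis has a narrower FAS that requires a dose and would exclude them; SAP 4.5 and Protocol 9.2 do not.

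**Site should be added too.** It is in the analysis model, so the same logic seems to apply. But about 20 sites are planned. Even pooled, they could add many terms to every equation, and the SAP already provides fallbacks that discard predictors if the model fails to converge. A site term is a debatable trade-off and is not asked for here.

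**Conclusion.** The point holds for the imputation step only. Its treatment variable conflicts with the randomised-treatment estimand and with the FAS rule, is undefined for never-dosed FAS members, and makes the placebo reference group received placebo. Baseline psychotherapy is missing from a model whose output is analysed with it.

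The expected effect is small: about 0.005 in ordinary simulated scenarios and about 0.03 under an arm-specific psychotherapy dropout pattern that the documents do not predict. The direction of that larger shift follows from the sign assumed; the reverse pattern would be expected to push the other way. These sizes rest on the assumed psychotherapy share and effect, site spread, dropout mechanism and misdosing counts, and on a comparator that also included site.

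A reader might take this as a threat to the primary result. It is not one: the primary mixed model, the alpha and the sample size are untouched. What is at stake is whether a gap between the sensitivity and primary results can be interpreted.

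**What to change.** In SAP 5.1.1.1:

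1. Define `trt` in PROC MI as the randomised arm, TRT01P.
2. State that the placebo-only run takes randomised placebo as its reference.
3. Add psychotherapy at baseline to the `class` and `var` statements and to each `fcs` equation. The 5.1.1 code names this variable PSYBLFL and its covariate list PSYBLYN, so use one name.
4. Choose between imputation separately by arm (SAP 4.6) and imputation on all participants across arms (SAP 5.1.1.1), and make the code match.

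Do not require a site term.

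The cost is a few words of text and code, no new data, and one extra term or so per imputation equation. Protocol 9.5 allows the SAP to be amended before unblinding; after database lock, the change would be documented and justified in the CSR or an SAP addendum.

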5.1.2 Primary Efficacy Variable - BPDCL

The analysis of Total BPDCL will be the same as described in Section 5.1.1 for CGI-S A/A, except that no categorical summary table will be provided.

5.1.3 Secondary Efficacy Variables

For the secondary efficacy variables, Borderline Evaluation of Severity over Time (BEST), Beck Depression Inventory – II (BDI-II), State-Trait Anxiety Inventory (STAI) and State-Trait Anger Expression Inventory 2 (STAXI-2).

The following will be the primary variables used for statistical analysis and/or summary for each of the tests:

- BDI-II: Total Score
- BEST: Score (sum) for each of the individual 3 sub-categories (thoughts and feelings, behaviors [negative], behaviors [positive]), Total Score
- STAI: S-Anxiety and T-Anxiety Raw Scores
- STAXI-2: State Anger Scale Raw Score, Trait Anger Scale Raw Score and AX Index Raw Score

Summary statistics for each of those items will be presented by treatment and visit using the FAS. Mean scores (\pm standard deviation) will be presented by treatment.

The same MMRM as described in Section 5.1.1 will be calculated for secondary efficacy variables which are scheduled to be collected at *Weeks 8-12* (e.g., for STAI only S-Anxiety is collected at each visit), except that there will not be a formal significance test for the difference between treatments at *Week 12* and that no sensitivity analysis is planned for these endpoints. The differences from baseline at each week will be reported, including a 95% confidence interval.

The answers for each test item will be listed by subject and scores will be presented in a separate listing.

The results for all other efficacy assessments mentioned in Section 7.2 of the protocol will be listed and summarized by treatment/Visit.

5.2 Safety Evaluation

All safety summaries and analyses will be based upon the SAF as defined in Section 4.5.

5.2.1 Extent of Exposure

The total dose taken will be estimated using compliance data, by taking the difference of dispensed vs returned caps. Exposure will not be calculated for patients with an unknown number of returned caps.

Target Engagement and pharmacokinetic (C_{trough}) values will also be summarized by treatment and visit. A listing for Target Engagement and C_{trough} values will be presented.

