TITLE OF THE STUDY 
“A double blind, randomized, placebo-controlled, adaptive 14-week Phase IIb trial to evaluate the efficacy and safety of vafidemstat in an adult borderline personality disorder (BPD) population (PORTICO)”
	
OBJECTIVES Primary Objectives 
 To investigate the efficacy of vafidemstat in the treatment of agitation and aggression in adult BPD patients To investigate the efficacy of vafidemstat in the treatment of adult BPD patients Secondary Objectives 
 To investigate the effect of vafidemstat in reducing the severity of BPD symptoms in adult patients To evaluate the safety of vafidemstat in adult BPD patients Exploratory Objectives 
 To explore the impact of vafidemstat on functional impairment in adult BPD patients To explore the impact of vafidemstat on cognition in adult BPD patients To evaluate vafidemstat plasma concentrations (pharmacokinetics) as well as vafidemstat’s LSD1-target engagement in peripheral blood mononuclear cells (PBMCs) (pharmacodynamics) after treatment 	
OVERALL STUDY DESIGN 
PORTICO is a double blind, randomized, placebo-controlled, adaptive 14-week Phase IIb trial to evaluate the efficacy and safety of vafidemstat in an adult borderline personality disorder (BPD) population. The trial is designed to help inform potential future trials and registration efforts.
 
Up to 188 participants will be enrolled and randomized in a 1:1 ratio (94 participants per arm) to active treatment with vafidemstat (1.2 mg) or placebo to yield an expected 150 completed study participants, since it is anticipated that 20% of participants will drop out of the trial. The sample size may be adjusted upwards based on the outcome of the interim analysis.
 
PORTICO will involve 9 study visits as reflected in the Schedule of Assessments and Procedures (Table 1). There will be a two-week screening period to ensure study eligibility criteria, followed by 12-week double-blind period of active treatment (vafidemstat 1.2 mg/day) or placebo with study visits every two weeks, then a 2-week safety follow-up participant-blind placebo run-out period (Figure 1).
 
The study treatment, vafidemstat or placebo, will be administered orally as single capsule in the early morning before the first daily food intake. Participants will be asked to maintain a stable regimen of
	

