- (9) Blood extractions should ideally take place at the same time of the day and in fasting conditions (e.g., preferably, first thing in the morning) in order to allow participants to ingest food before going on with the rest of study assessments. In case the study visit is scheduled in the afternoon/evening, fasting conditions will only be required at Visit 2 (Baseline), Visit 4, Visit 6 and Visit 8. Fasting conditions should last 6-8 hours. All blood samples will be collected prior to study drug intake at all study visits.
- (9i) For US Sites ONLY: C_{max} will be assessed in a subset of participants. In these participants, one extra blood sample for PK assessments will be obtained 1 to 2 hours after IMP intake on Visits 4 and 6 (in addition to the pre-dose sample already scheduled on these visits). Participants will have to sign a separate specific informed consent form.
- (10) As blood sampling for the exploratory assessments is an integral part of the study, the main Patient Information Sheet covers these analyses
- (11) Study treatment will be dispensed at each study visit from Visit 2 to Visit 8. Each dispensation will consist in a box containing the treatment for 14 ± 2 days. At each visit, the first study drug intake, corresponding to the new treatment box dispensed on that visit, should occur at the clinic in fasting conditions, however If the study visit is scheduled in the afternoon/evening, no fasting conditions are required before IMP intake at the clinic .
- (12) ONLY APPLICABLE IN CASE THE PARTICIPANT IS RECEIVING CONCOMITANT TREATMENT WITH ANTIDEPRESSANTS (i.e., selective serotonin reuptake inhibitors, serotonin-norepinephrine reuptake inhibitors, tricyclics, tetracyclics, and triazolopyridines): A follow-up call will be required approximately 6-8 hours post first IMP administration, as well as at 24 hours and 48 hours to ensure participants are not experiencing any signs or symptoms of serotonin syndrome. If a participant is experiencing moderate symptoms of serotonin toxicity such as agitation, tachycardia, diaphoresis, and/or hyperthermia, then they will immediately be referred to local emergency services.

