5. STUDY TREATMENT

5.1. Investigational Medicinal Product

5.1.1. Treatment Regimens

During the 12-week, double-blind, randomized, placebo-controlled *Treatment period*, from Visit 2 to Visit 8, participants will be randomized to one of these two treatment arms:

- Vafidemstat 1.2 mg/day fiw: participants will receive 1 capsule with 1.2 mg/day of vafidemstat from Monday to Friday and 1 capsule of placebo from Saturday to Sunday.
- Placebo: participants will receive 1 capsule of placebo per day.

During the 2-week, participant-blind, *Run-out Safety follow-up period*, from Visit 8 to Visit 9, all participants will receive 1 capsule of placebo per day.

Participants will be instructed to take the IMP orally as a single capsule, in the early morning before the first food intake (after overnight fasting conditions), once daily.

When attending planned study visits, participants must return to the investigator all the empty, partially used or unused blisters as well as the box and must take the IMP from the new box dispensed at the clinic, after all the corresponding blood extractions have been performed.

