5.1.3. Packaging and Labelling of Investigational Medicinal Product

Secondary packaging, labelling, including blinding of drug and placebo products will be performed by [REDACTED]. Medication label will follow the EU rules in Annex 13 of the GMP guidelines and the US CFR Title 21 – Part 210.

It is the responsibility of the Sponsor to guarantee that the samples of the clinical trial will be supplied to the investigative center correctly labelled according to Annex 13 of the GMP of the EU and CFR Title 21 – Part 210 of the US. The Sponsor can delegate this function to the elaborating entity of the samples, the CRO or to the pharmacy service of the centers.

Medication will be packed in 14-day treatment boxes. Each 14-day treatment box will contain 3 blisters with 5 active or placebo capsules and 3 more blisters identified as Saturday and Sunday containing 2 placebo capsules each. Therefore, the whole study treatment for a participant will be composed by seven 14-day treatment boxes to be dispensed individually at each study visit. Each box contains a sufficient number of capsules to cover the period between visits as per study protocol, including the window period (± 2 days).

The wording on the labels will be in accordance with Good Manufacturing Practice regarding labelling and national and/or local regulatory requirements.

No manipulation, repackaging, or relabeling of IMP is permitted after QP release by the IMP supplier unless a repackaging/relabeling agreement exists, and the documentation is available to [REDACTED] and, where necessary, new QP releases are made.

Each of the treatment boxes will be identified using a unique kit number. The study medication must be stored in a safe and secure location, and in accordance with the storage conditions specified on the label.

The details of the secondary packaging and the instructions for the IMP intake are available in a separate Pharmacy Manual.

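### The total dose in SAP 5.2.1 counts placebo capsules, so it is not vafidemstat dose; at 1.2 mg per capsule it would overstate a fully adherent participant's dose by 40% to 63%

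*SAP*

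**What the plan says.** SAP 5.2.1 (Extent of Exposure) gives one rule: "The total dose taken will be estimated using compliance data, by taking the difference of dispensed vs returned caps". It states no unit and no mg conversion, and it leaves exposure uncalculated when the number of returned capsules is unknown. SAP 4.11, which supplies the compliance data, also works with a pooled count and does not split capsules by blister.

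Protocol 5.1.1 defines the active regimen: "participants will receive 1 capsule with 1.2 mg/day of vafidemstat from Monday to Friday and 1 capsule of placebo from Saturday to Sunday". For the run-out between Visit 8 and Visit 9 it says that "all participants will receive 1 capsule of placebo per day".

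Protocol 5.1.3 describes the pack: "Each 14-day treatment box will contain 3 blisters with 5 active or placebo capsules and 3 more blisters identified as Saturday and Sunday". The weekend blisters hold two placebo capsules each. The whole course is "composed by seven 14-day treatment boxes to be dispensed individually at each study visit", and footnote 11 to Protocol Table 1 confirms: "Study treatment will be dispensed at each study visit from Visit 2 to Visit 8". The run-out box is therefore among the capsules dispensed, and Table 1 schedules a compliance count at Visit 9.

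**The concern.** A pooled count of unreturned capsules is a sound measure of adherence, because the placebo capsules are also meant to be taken. It does not measure dose when a fixed share of the capsules in the active arm, and one whole box, contain no drug.

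At stake is the cumulative exposure figure that accompanies the safety results. Readers will set it beside the haematology findings, since platelet and neutrophil decreases are the adverse events of special interest. A figure that includes placebo capsules would suggest that tolerability was observed at a higher cumulative dose than was given. Readers also could not rescale it by one factor. Non-completers do not enter the run-out, so the discrepancy differs by completion status, and it further depends on which capsules were missed.

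**Working it through.** **Inputs**
- Active capsules per week: 5, each 1.2 mg (Protocol 5.1.1).
- Placebo capsules per week in the active arm: 2 (Protocol 5.1.1).
- Treatment period: 12 weeks, Visit 2 to Visit 8 (Protocol Synopsis and 5.1.1).
- Run-out: 2 weeks, one placebo capsule a day, so 14 capsules (Protocol 5.1.1).
- Box: 3 × 5 weekday + 3 × 2 weekend = 21 capsules, including spares for the visit window (Protocol 5.1.3).

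**The plan's own figure.** The documents state no total dose in mg. The figure that can be checked is the number of boxes: 14 weeks / 2 weeks per box = 7, which agrees with Protocol 5.1.3 and with dispensing at Visits 2 to 8. Six boxes cover treatment and the seventh is the run-out.

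**Fully adherent participant, vafidemstat arm**
- Drug taken: 12 × 5 = 60 active capsules; 60 × 1.2 = 72.0 mg.
- All treatment-period capsules at 1.2 mg: 12 × 7 = 84; 84 × 1.2 = 100.8 mg; 84/60 − 1 = 40.0%.
- Adding the run-out box: 84 + 14 = 98; 98 × 1.2 = 117.6 mg; 98/60 − 1 = 63.3%.

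**Sensitivity**
- Even adherence of 80% or 90% cancels from the ratio: (84 × 0.8)/(60 × 0.8) is still 1.40, and 98/60 is likewise unchanged.
- Varying the weekday of the first dose and the ±2-day windows at Visits 8 and 9 moves individuals to about 37–43% without the run-out box and 55–72% with it.
- Very short exposures can fall outside these ranges: over 5 days the overstatement is 0% to 67%, depending on the start day.
- Arm level, assuming that the planned 20% dropout all occurs at week 6: (0.8 × 98 + 0.2 × 42)/(0.8 × 60 + 0.2 × 30) − 1 = 86.8/54 − 1 = 61%. The timing is an assumption; the documents give only the 20%.

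**The same count can hide different doses.** A participant who takes all 84 treatment-period capsules and stops at Visit 8 has received 72.0 mg. A completer who misses 14 weekday capsules during treatment also shows 98 − 14 = 84 capsules, but has received 46 × 1.2 = 55.2 mg.

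**The case against.** The strongest objection is that this is an underspecified sentence and not a wrong number. SAP 5.2.1 gives no unit, and neither document states a total dose. A capsule count is a plausible reading, because the sentence covers both arms and the placebo arm has no mg dose. The note to SAP Figure 1 also says that placebo is taken on the two days off, so a careful programmer could exclude those capsules. Much of this stands: the percentages depend on counting 1.2 mg per capsule. But the section calls the result the total dose taken, and the figure note does not alter the rule. A bare capsule count would still carry the wrong label.

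A reader might also infer that this total is the denominator for the platelet and neutrophil results. The documents do not support that. SAP 5.2.2 tabulates those events by patients and events per treatment, SAP 5.2.4 summarises laboratory values by treatment and visit, and no per-mg or cumulative-dose analysis is planned.

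Drug exposure is also assessed without capsule counts. Protocol 9.3.9 uses target engagement, and SAP 5.2.1 itself summarises target engagement and trough concentrations. This stands and limits the consequence.

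Finally, SAP 4.8 already reports what was found at the interim analysis, so a new accountability field might not recover earlier counts. This also stands, and it shapes the fix.

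**Conclusion.** The point holds as a defect in one descriptive safety summary. Followed literally, the rule in SAP 5.2.1 does not yield vafidemstat dose in the active arm, and nothing elsewhere in the SAP or protocol corrects it.

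The size is conditional. With 1.2 mg assigned to every unreturned capsule, whole weeks of treatment and even adherence, the overstatement is 40% for the treatment period and 63% for completers whose run-out box is counted. It would go too far to say that the reported exposure will be wrong by that amount for every active-arm participant. The SAP does not prescribe the conversion, participants with unknown returns get no value, only those who enter the run-out can reach 63%, and individual values vary as shown. Target engagement, trough concentration, adverse event, laboratory and efficacy analyses are unaffected. The SAP should be corrected because the rule is explicit, the result is a safety exposure figure, and the remedy is cheap.

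**What to change.** In SAP 5.2.1, define total vafidemstat dose as 1.2 mg × (weekday-blister capsules dispensed minus returned), summed over the boxes dispensed at Visits 2 to 7, for the vafidemstat arm only. Count weekend blisters and the Visit 8 box as 0 mg. Report the pooled capsule count separately and call it adherence.

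Use returns by blister type where source records or the eCRF hold them. The eCRF and Pharmacy Manual are not among the documents, so this needs checking. Otherwise leave out the Visit 8 box, split each pooled count in proportion to the weekdays and weekend days in its dispensation interval, and flag the value as estimated. For a fully adherent 14-day interval this gives 14 × 10/14 × 1.2 = 12 mg, and six intervals give the correct 72 mg.

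The cost is SAP wording and a short derivation; no new eCRF field or site procedure is required. Both arms share the blister layout, so counting by blister does not unblind. The downside is that allocated values are approximate when missed capsules are uneven. In the example with 14 missed weekday capsules, 84 − 14 = 70 treatment-period capsules would be allocated as 70 × 5/7 × 1.2 = 60.0 mg against a true 55.2 mg. That is why the flag is needed.
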